Ethnic and racial minority recruitment is expected to occur in the same rate as in the local community. The racial and ethnic make-up of the present study is expected to reflect the community make-up, with approximately 75% of subjects identifying themselves as Caucasian, 15% as African-American, 4% as Asian, and 6% as Hispanic or Latino. Ethnic diversity status will be determined at the intake session by responses on the demographic questionnaire, in accordance with the categories set forth by the OMB guidelines. No one will be excluded based on ethnic or racial minority status. Should participation of minority groups fall below representative levels we will focus advertisements in primarily African-American groups and organizations on the college campus and in the surrounding community. Proposed outreach programs include formal advertisement (i.e., regular newspaper advertisements placed generally in free newspapers and radio messages), local flyers posted in public areas (e.g., bars and marketplaces), word-of-mouth, and the Internet. Such strategies have proved effective at increasing minority enrollment in previous research.

In order to obtain a sample of women who have completed puberty, have regularly-occurring cycles, and who have the same general life experiences, participants will be women between ages 21 and 35. All participants will complete the informed consent procedure before providing personal information. During the informed consent procedure, participants will be informed about study procedures, tasks, risks and benefits, and participants will be given an opportunity to ask questions before they provide written consent. Participants will be informed that they can withdraw from the research at any time.

Procedures and consent forms will comply with requirements of the University of Kentucky Institutional Review Board.

Exclusion Criteria:

- use of hormone-based medications (e.g., hormone-based birth control or steroids)
- known hormonal abnormalities (e.g., Polycystic Ovarian Syndrome, thyroid conditions)
- irregular menstrual cycles (i.e., varying by more than 10 days between cycles; any cycle less than 25 days or over 35 days in length, as indicated by self report of cycle length over past 3 months)
- current pregnancy
- primary sensorimotor handicap
- frank neurological disorder (e.g., seizure disorders, brain tumor, cerebral palsy, hydrocephalus, head injury with loss of consciousness)

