Subjects will attend a diagnostic visit to assess baseline clinical characteristics. In addition, subjects will attend two laboratory visits to test alcohol sensitivity at two key points in the cycle: during the early follicular phase when E2 is low and the late follicular phase when E2 is rising. Every day after their first laboratory visit for 35 consecutive days, women will provide saliva samples each morning to assess hormonal levels and complete a self-report on their drinking behavior and alcohol craving every evening through a secure online server.

The daily saliva and self-report data will allow for a fine-grained investigation of the lagged correlations between E2 and daily alcohol use patterns and alcohol craving across the entire menstrual cycle. The two laboratory visits will test and compare the acute sensitivity to the rewarding and disinhibiting effects of a controlled dose of alcohol during the early follicular phase when E2 is low and the late follicular phase when E2 is rising. After screening, study volunteers will be followed daily in order to assess when they start their next menstrual cycle (i.e., the day they start bleeding). Within 1-2 days of that point, volunteers are scheduled to attend their initial diagnostic visit. Participants are then counterbalanced to begin the study during either their early follicular phase (approximately day 5) or their late follicular phase (approximately day 12) which is also when they begin their 35 days of consecutive daily data collection. This serves to counterbalance the order of the two alcohol sensitivity test sessions: early follicular versus late follicular phase. Ovulation testing and daily salivary E2 will confirm the proximity of the late follicular phase to ovulation, with the goal of ovulation occurring 1-3 days after the late follicular visit, and capturing a higher, rising E2 level in the late follicular phase relative to a lower level in the early follicular phase. We overrecruit in order to assure analyses are appropriately powered and reliable.

Attachments

Subject Recruitment Methods & Advertising

Describe how the study team will identify and recruit subjects. Please consider the following items and provide additional information as needed so that the IRB can follow each step of the recruitment process.

- How will the study team identify potential participants?
- Who will first contact the potential subjects, and how?

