When the participant starts their next cycle, their two alcohol sensitivity test sessions (early and late follicular tests) are scheduled with test order counterbalanced across participants. The early follicular phase lab visit will be scheduled on day 5 of their cycle. The late follicular phase lab visit will be scheduled based on self-reported onset of menses and their self-reported average cycle length using the following formula: (self-reported typical cycle length - 14 days of luteal phase = typical follicular phase length) * 0.85. This formula produces a day that is toward the end of the participant's typical follicular phase, when E2 will be rising sharply just prior to ovulation, and has resulted in minimally burdensome detection of ovulation in our previous studies. For a typical 28-day cycle, this would be approximately day 12. In order to confirm that the cycle is ovulatory and the proximity of the late follicular visit to ovulation, women will complete urine ovulation testing following their late follicular visit, described below. Participants provide multiple contacts (phone, text, email) for visit reminders.

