For the 35 days of daily data collection, starting the day after the first counterbalanced laboratory visit, participants provide saliva samples each morning approximately thirty minutes after waking and then store samples in their home freezers. Several procedures and quality control checks will be implemented to ensure rigorous and reliable data collection. During days 12-25, participants will take urinary ovulation tests each morning and submit the results. Every evening between 6 and 10 pm, they are instructed to log onto a secure website to complete a brief set of questions about their alcohol intake and alcohol craving (detailed below) which are time- and date-stamped so accuracy of data collection can be monitored. Participants receive twice daily reminders about data collection, and they are texted if they miss more than 2 consecutive days of data collection. Compliance with data collection procedures will be facilitated through incentives, a procedure that was piloted with success during preliminary data collection. Participants will be paid up to \$440 for complete data collection, but will lose \$5 for every missed survey. At the end of the 35 days, study staff contact participants and arrange for a time for them to return their saliva samples to the laboratory for storage in a -80 degree freezer, as well as receive their payment. Following the end of data collection, saliva samples are sent in bulk to the Center for Clinical and Translational Science (CCTS) on the University of Kentucky campus for at-cost assay.

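### One fixed urine-testing window (days 12–25) for all women, with no day type stated: read as cycle days, it opens too late for 25–26 day cycles because the late-follicular visit moves with cycle length

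*Combined protocol and SAP*

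**What the plan says.** Four parts of the combined protocol and SAP bear on this point.

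- **Exclusion Criteria** rule out "any cycle less than 25 days or over 35 days in length", so eligible lengths run from 25 to 35 days.
- **Research Procedures, scheduling paragraph**, sets the late-follicular visit by formula: "self-reported typical cycle length - 14 days of luteal phase = typical follicular phase length) * 0.85". It adds an example: "For a typical 28-day cycle, this would be approximately day 12". To confirm that the cycle is ovulatory and that the visit was close to ovulation, "women will complete urine ovulation testing following their late follicular visit".
- **Research Procedures, daily-collection paragraph**, gives the testing schedule: "During days 12-25, participants will take urinary ovulation tests each morning and submit the results". The paragraph opens with the 35 days of collection, which start the day after the first laboratory visit. It does not say whether days 12–25 are cycle days, collection days or a nominal label, and no other section supplied defines them.
- **Study Design** states the timing goal, "with the goal of ovulation occurring 1-3 days after the late follicular visit", and the means of checking it: "Ovulation testing and daily salivary E2 will confirm the proximity of the late follicular phase to ovulation".

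**The concern.** The visit is individual and the test window is not. If the window counts cycle days, it cannot follow a visit whose date shifts by more than a week across the eligible lengths. In short cycles, the days on which the plan hopes to see ovulation can pass before the first test.

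Hypothesis 2 depends on the late session falling just before ovulation, and urine testing is one of the two stated ways to check this. In a short cycle, the absence of a positive test might mean only that testing began late. Treating such a cycle as anovulatory, or its session as mistimed, would be unsafe.

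**Working it through.** **Inputs.** Cycle length L = 25 to 35 (Exclusion Criteria). Visit day = 0.85 × (L − 14) (scheduling paragraph). Target days = visit + 1, + 2 and + 3 (Study Design). Window = cycle days 12 to 25, which is 25 − 12 + 1 = 14 mornings.

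**Assumptions.** The plan does not state a rounding rule, so I round the visit to the nearest day. I count a target day as covered if a test is scheduled for that morning.

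**The plan's own figure.** At L = 28: 0.85 × 14 = 11.9, or day 12, as the example says.

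**All eligible lengths, cycle-day reading:**

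| L | 0.85 × (L − 14) | Visit day | Target days | Untested target days | Test mornings before the visit day |
|---|---|---|---|---|---|
| 25 | 9.35 | 9 | 10–12 | 10, 11 | 0 |
| 26 | 10.20 | 10 | 11–13 | 11 | 0 |
| 27 | 11.05 | 11 | 12–14 | none | 0 |
| 28 | 11.90 | 12 | 13–15 | none | 0 |
| 29 | 12.75 | 13 | 14–16 | none | 1 |
| 30 | 13.60 | 14 | 15–17 | none | 2 |
| 31 | 14.45 | 14 | 15–17 | none | 2 |
| 32 | 15.30 | 15 | 16–18 | none | 3 |
| 33 | 16.15 | 16 | 17–19 | none | 4 |
| 34 | 17.00 | 17 | 18–20 | none | 5 |
| 35 | 17.85 | 18 | 19–21 | none | 6 |

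The loss is 2 of 3 target days at 25 days and 1 of 3 at 26 days.

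**The formula's own follicular length.** L − 14 is day 11 at 25 days, one day before the first test. At 26 days it is day 12, the first test morning. From 27 days it lies inside the window.

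**Sensitivity to rounding.**
- Up: the visit is day 10 at 25 days (targets 11–13, 1 of 3 missed) and day 11 at 26 days (targets 12–14, none missed). This also fits the 28-day example.
- Down: 2 of 3 and 1 of 3, as with nearest-day rounding. But it puts the 28-day visit on day 11, against the stated example.
- Day 11 at 25 days is untested under every rule.

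**Long cycles.** At 29–35 days, testing starts 1 to 6 days before the visit. That conflicts with the statement that testing follows the visit, but no target day is lost.

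**Nominal reading.** If day 12 stands for the individual visit, the window is 14 mornings from the visit, which covers visit + 1 to + 3 at every length. Nothing is missed.

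**The case against.** The best defence is that day 12 is shorthand. Study Design describes women starting in "their late follicular phase (approximately day 12") although the visit is set by formula, and the Initial Diagnostic Visit paragraph has home data entry begin on day 5 or day 12 for everyone. The scheduling paragraph says that testing follows the visit and points forward to its description. On that view, days 12–25 mean 14 mornings from the individual visit and there is no gap. This stands as a possible reading. But the daily-collection paragraph does not state it, and a woman or coordinator following the words literally would count cycle days.

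Three stronger conclusions might be inferred, and the documents do not support them.

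- **That days 12–25 are collection days, so that most target days are lost.** Late-first women would then start testing 12 days after the visit and miss 33 of 33 target days (3 days × 11 lengths). Early-first women would miss 20 of 33 if collection starts on cycle day 6, or 16 of 33 if it starts on day 5. But the neighbouring text counts in days of the cycle, so this reading is unlikely, and the early-first count depends on the start day assumed.
- **That the early start at 29–35 days harms the study.** It is a wording conflict only, with no loss of coverage.
- **That cycles will be misclassified.** No supplied passage codes a cycle as anovulatory, or a session as mistimed, from a missing positive test, and Study Design pairs urine testing with daily salivary E2. The risk is that nothing in the text prevents it.

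The written at-home instructions and the grant are not among the documents supplied and may settle the day type.

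**Conclusion.** The mismatch between the scheduling and daily-collection paragraphs is real, and its effect is minor. On the cycle-day reading with nearest-day rounding, the window leaves 2 of 3 target days untested at 25 days and 1 of 3 at 26 days. Rounding up reduces this to 1 of 3 and 0 of 3. Lengths 27–35 lose nothing. On the nominal reading no length does.

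The most robust part is the 25-day case: the formula's own expected ovulation day comes before the first test whichever way the visit is rounded. The size of the effect in the sample cannot be computed, because the share of women with 25–26 day cycles is not given. These lengths sit at the short edge of eligibility, and salivary E2 gives partial cover.

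**What to change.** **Text.** In the daily-collection paragraph, replace the fixed days with wording such as: *Participants take a urinary ovulation test on 14 consecutive mornings, starting no later than the morning after the individually scheduled late-follicular visit.* With the start placed on that morning, testing runs from visit + 1 to visit + 14. With nearest-day rounding this is cycle days 10–23 at a 25-day length, 11–24 at 26 days, 13–26 at 28 days and 19–32 at 35 days. It covers all three target days at every eligible length and agrees with the scheduling paragraph. For late-first women it begins on the day collection opens. State the rounding rule for the visit in the same edit.

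**Data already collected.** The Continuation Review section reports 136 enrolled to date, so this part matters too.
- State which day type the at-home instructions used.
- Where the first test came later than the day after the late-follicular visit, do not treat the lack of a positive test alone as showing an anovulatory cycle or a mistimed session. Use salivary E2 and, where recorded, the onset of the next menses.
- The menses check is feasible in principle. Expected onset on day L + 1 (days 26–36) falls within the 35 collection days for both orders: cycle days 6–40 for early-first women, and visit + 1 to visit + 35 for late-first women.

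**Cost.** One revised sentence, one stated rounding rule and one classification rule. The number of tests stays at 14. The downside is an individual start date for test reminders, and the menses check works only where the date was recorded.

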- If you are conducting greater than minimal risk research, or your clinical investigation is NIH-funded, describe your Data and Safety Monitoring Plan (DSMP). [Click here for additional guidance on developing a Data and Safety Monitoring Plan.](#)
- If this is a non-sponsored investigator-initiated protocol considered greater than minimal risk research, and if you are planning on using a Data and Safety Monitoring Board (DSMB) as part of your DSMP, [click here for additional guidance](#) for information to include with your IRB application.

Drs. [name] and [name] will be responsible for monitoring the safety of the study, executing the DSMP, and complying with the reporting requirements. PI [name] will provide a summary of the DSM report for NIAAA as part of the annual progress report. The DSM report will include the subject sociodemographic characteristics, expected versus actual recruitment rates, retention rates, any quality assurance or regulatory issues that occurred during the past year, summary of serious adverse events (SAEs), and any substantial actions or changes with respect to the protocol. The DSM report will also include, if applicable, the results of any data analysis conducted.

Data Monitoring Plan:

For the daily assessment of hormonal levels, ovulation, and drinking behavior, several procedures and quality control checks will be implemented to ensure rigorous and reliable data collection. These include daily monitoring of subjects' reporting on the collection/storage of saliva samples, drinking patterns, and urinary ovulation tests. Data is transferred via secure website that time- and date-stamps data so accuracy of data collection can be monitored. Data from experimental sessions will be collected using a computerized data collection and management system. All data are stored in a unique file on the hard-drive of the computer and are electronically backed-up at the end of each session. In all instances, the data files do not contain the name of the subject; but instead,

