Potential subjects will provide information regarding their alcohol and other drug use and medical history to determine their eligibility and the safety of their participation. Individuals with past or current serious physical or mental health conditions are contraindicated for study participation. Subjects must not be nursing, and must test negative for pregnancy prior to each experimental session. Potential subjects who report regular use of any psychotropic medication will be excluded. Methods for monitoring adverse events (AEs) will include observations by research staff, spontaneous report by the subjects, regular measurement of subjective-effects and performance on experimental tasks. All AEs occurring during the course of the study will be collected, documented, and reported to the investigators and the study physician following each occurrence. The occurrence of AEs will be assessed daily for the duration of participation and as needed in follow-up visits as appropriate. The investigators and study physician will follow all AEs to the point of a satisfactory resolution. Subjects may be withdrawn from the study if the investigators determine it is the best decision in order to protect the safety of the subject. All AEs will be assessed to determine if they meet criteria for a serious adverse event (SAE). SAEs, as defined by the FDA, will be systematically evaluated daily for the duration of participation and as needed in follow-up visits as appropriate. Any SAE will be reported to the IRB and NIAAA. In the event that a subject either withdraws from the study or the investigator decides to discontinue a subject due to an SAE, the subject will have appropriate follow-up medical monitoring. A summary of the SAEs that occurred during the previous year will be included in the annual progress report to NIAAA.

Data and Safety Monitoring Board:

NIH requires the establishment of a Data and Safety Monitoring Board (DSMB) for 1) multi-site clinical trials involving interventions that entail risk to the participants and 2) for most Phase III clinical trials. This project meets neither of these definitions and therefore, a DSMB is not required and will not be utilized.

[Back to Top](#)

Future Use and Sharing of Material (e.g., Data/Specimens/Information)

If the material collected for this study will be used by members of the research team or shared with other researchers for future studies, please address the following:

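### Daily AE and SAE assessment is promised for the whole of participation, but no described procedure asks about AEs on the 33 or 34 of 35 diary days without a laboratory visit

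*Combined protocol and SAP*

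**What the plan says.** The Safety Monitoring Plan (under Data and Safety Monitoring) makes three commitments:

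- On AEs: "The occurrence of AEs will be assessed daily for the duration of participation".
- On SAEs: "SAEs, as defined by the FDA, will be systematically evaluated daily for the duration of participation".
- On completeness: "All AEs occurring during the course of the study will be collected, documented, and reported to the investigators and the study physician following each occurrence".

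It then gives the means: "Methods for monitoring adverse events (AEs) will include observations by research staff, spontaneous report by the subjects", followed by regular subjective-effects measurement and performance on the experimental tasks.

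Research Procedures describes the at-home period. Each evening women log on to "complete a brief set of questions about their alcohol intake and alcohol craving". They collect saliva each morning, submit ovulation test results on days 12-25 and receive reminders twice a day. On non-response, "they are texted if they miss more than 2 consecutive days of data collection".

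The Data Monitoring Plan describes daily staff checks as "daily monitoring of subjects' reporting on the collection/storage of saliva samples, drinking patterns, and urinary ovulation tests". The DSM report to the funder lists, among other items, a "summary of serious adverse events (SAEs)". It does not list non-serious AEs.

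**The concern.** A plan that promises daily, systematic assessment should contain a procedure that carries it out. Here the procedure is visible at the laboratory sessions but not on the days between and after them. That stretch includes the hours after release from an alcohol session, when women are cautioned about their activities and told not to drive until the next morning.

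The application records Risk Level 3 and states that no DSMB will be used, so the monitoring plan is the main safety safeguard. If AEs at home are recorded only when a woman volunteers them, counts will tend to be low and dates late. A reader of the safety summary could take the promised daily assessment at face value and give a short list more weight than it deserves.

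**Working it through.** The plan gives no figure to reproduce. The check is a count of days, followed by a comparison of methods with settings.

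**Inputs**

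- Diary length: 35 days (Study Design; Research Procedures).
- Diary start: the day after the first laboratory visit (Research Procedures, and one sentence of Study Design), or at the first test phase itself (another sentence of Study Design). Both are used below.
- Early visit: cycle day 5. Late visit: (cycle length − 14) × 0.85 (Research Procedures).
- Eligible cycle length L: 25 to 35 days (exclusion criteria).
- Visit order: counterbalanced.

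**Gap between the two visits**

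Late visit day = round((L − 14) × 0.85). If early comes first, gap = late day − 5. If late comes first, the early visit falls on day 5 of the next cycle, so gap = L + 5 − late day.

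| L | (L − 14) × 0.85 | Late day | Gap, early first | Gap, late first |
|---|---|---|---|---|
| 25 | 9.35 | 9 | 4 | 21 |
| 28 | 11.90 | 12 | 7 | 21 |
| 35 | 17.85 | 18 | 13 | 22 |

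Over all L from 25 to 35 the gap is 4 to 13 days (early first) or 21 to 22 days (late first). Visit 2 therefore always falls inside the diary.

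**Diary days with no laboratory visit**

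- Start the day after visit 1: only visit 2 is inside, so 35 − 1 = 34 (34/35 = 97%).
- Start on the day of visit 1: both visits are inside, so 35 − 2 = 33 (33/35 = 94%).
- For 100 women this is 3,300 to 3,400 of 3,500 diary days.
- If an early-first woman's late visit slipped to the next cycle (an assumption), the gap would be L + late day − 5: 29 days for L = 25, 35 for L = 28 and 48 for L = 35. Visit-free diary days could then reach 35.

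**Diary days left after the second dose**

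With the day-after start, visit 2 falls on the diary day equal to the gap. The remainder is 35 − 13 = 22 to 35 − 4 = 31 days (early first), or 35 − 22 = 13 to 35 − 21 = 14 days (late first). The other start rule gives one day fewer.

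**Which listed method works on those days?**

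| Method in the Safety Monitoring Plan | Described setting | Works at home? |
|---|---|---|
| Staff observation | Laboratory sessions | No |
| Subjective-effects measures | Laboratory sessions, 11 times at 30-minute intervals | No |
| Task performance | Laboratory test battery | No |
| Spontaneous report | Anywhere | Yes, if the woman starts it |

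**Do the at-home contacts fill the gap?**

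- Evening survey: described as covering alcohol intake and craving.
- Saliva collection and ovulation results: samples and test results.
- Twice-daily reminders: about data collection.
- Telephone access to a research assistant, the investigators and the study physician, and 24-hour on-call support: the woman must call.
- Daily staff monitoring: saliva, drinking reports and ovulation tests.
- Daily investigator meetings: with project staff, who can pass on only what they have been told.

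**Where staff do make, or might make, a health enquiry**

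- Re-screening before each session covers general health status (Records, Privacy, and Confidentiality, Subject Screening). At visit 2 this gives one look back over the days since the first dose.
- An exit interview is offered and encouraged, but not required.
- Staff contact women after day 35 to arrange sample return and payment. No health question is described.

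These are a few points in time. They do not amount to daily assessment.

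**The case against.** The strongest reply is that the documents contain more than a quick reading suggests. Much of it stands, and it rules out several stronger readings.

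- **That at-home AEs go uncollected.** Spontaneous report is a named method, several telephone routes exist, and every woman who attends visit 2 is re-screened after her first dose. The supportable statement is incomplete or late ascertainment.
- **That the survey is the only contact.** Reminders, ovulation results and participant-initiated calls are also contacts. The narrower point holds: none is described as asking about AEs.
- **That non-serious AEs are never tabulated.** The IRB's continuing review form (item 4) asks for a written summary of available AE information. Only the DSM report's list is confined to SAEs. That list also admits results of any data analysis conducted.
- **That the missed-survey text is a faulty safety rule.** It reads as a data-compliance rule, applies to more than 2 consecutive missed days and comes on top of routine reminders. It neither supplies nor removes an AE enquiry.
- **That the laboratory's record of over 5000 participants predicts a blank SAE summary.** That record is per participant and concerns alcohol administration. It cannot be applied per session or used to bound SAEs over 35 days at home.
- **That the study could wrongly conclude AEs do not differ by phase.** Comparing AEs by phase is not among the aims. The dosing window itself is monitored in the same way in both phases.

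Two further objections carry weight. The survey form is not reproduced, and it is not among the attachments listed under Data Collection & Research Materials, so an AE item on it cannot be excluded. The change may also come late. The demographic table shows 2 + 8 + 3 + 72 + 10 = 95 women with recorded race, against a target of 100. If those 95 are the enrolled participants, which is an inference, a new item would reach few more women.

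Neither objection removes the mismatch between the promise and the procedures as written.

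**Conclusion.** The concern holds as a mismatch between a stated property of the safety plan and the procedures meant to deliver it. On 33 or 34 of 35 diary days the only listed method available is spontaneous report, which is neither daily nor systematic. AEs arising at home may be missed or reported late. How many cannot be estimated from the documents.

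The count assumes that visits follow the scheduling formula, rounded to whole days, and that visit 2 is not deferred to a later cycle. The conclusion assumes that the survey contains only what Research Procedures describes. If it already has a health item, what remains is to describe that item and add the AE table.

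This is worth correcting because it concerns safety ascertainment and is cheap to fix. It does not affect the analyses of the three aims.

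**What to change.** 1. Reconcile the Safety Monitoring Plan with Research Procedures. Unless the evening survey already has one, add a fixed item asking about any injury, illness or other health problem since the last report, with free text. The coordinator reviews responses the next day and passes positive ones to the study physician, in line with the existing commitment to report all AEs.
2. In the DSM report, tabulate all collected AEs by session and cycle phase next to the SAE summary. The same table can serve the IRB's continuing review.
3. If the item is not added, restate the Safety Monitoring Plan to say that AEs between visits are captured by passive reporting, with staff enquiry at the points where it actually takes place.

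The cost is one survey item, a short daily review and one table. Women spend a few more seconds a day, and some positive answers will prove unimportant. The item will cover only completed surveys, although asking about the time since the last report recovers isolated missed days. Active questioning will probably raise AE counts, so AEs before and after the change should be shown separately.
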